9.4.3 Prohibited concomitant therapy with BGJ398

CYP inhibitors

Strong inhibitors of CYP3A4 such as the ones listed in Appendix C are prohibited because BGJ398 is a likely substrate of this isoenzyme. Caution should be used during administration of moderate inhibitors. The following food products are prohibited: Seville oranges or juice, grapefruit, grapefruit juice, grapefruit hybrids, and pummelos.

CYP inducers: Strong inducers of CYP3A4 are prohibited because their usage would likely decrease the exposure of BGJ398. Therefore, agents such as those listed in Appendix E are prohibited. Caution should be used during administration of moderate inhibitors.

MEMORIAL SLOAN-KETTERING CANCER CENTER IRB PROTOCOL

IRB#: 14-140 A (7)

Phosphorus and calcium: Medications that increase the serum levels of phosphorus and/or calcium are prohibited. These include, but are not limited to, calcium, phosphate, vitamin D, parathyroid hormone (PTH).

Herbal medications: Herbal preparations/medications are not allowed throughout the study. These herbal medications include, but are not limited to: St. John's wort, Kava, ephedra (ma huang), ginkgo biloba, dehydroepiandrosterone (DHEA), yohimbe, saw palmetto, and ginseng. Patients should stop using these herbal medications 7 days prior to first dose of study drug.

Enzyme Inducing Anti-epileptic drugs (EIAEDs): Enzyme inducing anti-epileptic medication is not allowed (please refer to Appendix E). Patients who were previously on a non-EIAED and need to permanently change anticonvulsants, but who cannot change to another non-EIAED must be discussed with the MSKCC PI and Novartis. These patients will be taken off-study unless it is felt that they have benefited from the therapy following discussion with the MSKCC PI and Novartis.

10.0 EVALUATION DURING TREATMENT/INTERVENTION

10.1 Standard Evaluation

10.1.1 Study Calendar (Phase I Portion Study)

Baseline clinical evaluations are to be conducted within 2 weeks of starting protocol therapy. Radiologic evaluations and surgical biopsies must be done ≤ 4 weeks prior to the start of therapy.

Informed Consent can be obtained 30 days prior to the start of study therapy.

After patients have been on the combination therapy more than 4 cycles, the patient can increase the duration of the evaluation by the MD and RN to every 8 or 12 weeks at the investigator's discretion. The basic laboratory and EKG assessment between evaluations can be performed locally and will be obtained every 4 weeks for patients on the phase Ib portion of the study.

Table 9: Visit Evaluation Schedule during Phase Ib

MEMORIAL SLOAN-KETTERING CANCER CENTER
IRB PROTOCOL

IRB#: 14-140 A (7)

	Pre-Study	Cycle 1				Cycle 2				Cycle 3 and beyond				Off Study ^c
		Wk 1	Wk 2	Wk 3	Wk 4	Wk 5	Wk 6	Wk 7	Wk 8	Wk 9	Wk 10	Wk 11	Wk 12+	
Imatinib ^x		X	X	X	X	X	X	X	X	X	X	X	X	
BGJ398 ^{YA} Treatment Schedule A		YA	YA	YA		YA	YA	YA		YA	YA	YA		
BGJ398 ^{YB} Treatment Schedule B		YB				YB				YB				
Informed consent	X													
Demographics	X													
Medical history	X													
Concurrent Meds	X	X	X	X	X	X				X ^d				
Physical exam	X	X	X	X	X	X				X ^d				X
Vital signs	X	X	X	X	X	X				X ^d				X
Height	X													
Weight	X	X		X		X				X ^d				X
Eye Exam ^g	X				X									
Performance status	X	X	X	X	X	X				X ^d				X
CBC w/diff, plts ^l	X	X	X	X	X	X		X		X ^d				X
Urinalysis	X													
Blood chemistry ^{a,j}	X	X	X	X	X	X		X		X ^d				X
Hep B	X													
TSH	X							X		X ^d				
EKG	X			X		X				X ^d				
Echo or MUGA	X				X								X ^e	X

MEMORIAL SLOAN-KETTERING CANCER CENTER
IRB PROTOCOL

IRB#: 14-140 A (7)

Adverse event evaluation		X		X		X				X ^d				X
Radiologic evaluation	X									X ^f				X ^f
Tumor measurements	X									X ^f				
B-HCG	X ^b													
BGJ398 and imatinib PK Levels		X ^{h,i}		X ^{h,j}	X ^{h,i}									
	
X: Imatinib: Dose as assigned; PO once daily
 
YA: BGJ398: Dose as assigned; PO once daily for 3 weeks on and one week off
 
YB: BGJ398: Dose as assigned; PO once daily for one week on and 3 weeks off
 
a: Comp- Albumin, alkaline phosphatase, total bilirubin, bicarbonate, BUN, calcium, chloride, creatinine, glucose, potassium, total protein, SGOT [AST], SGPT [ALT], sodium. In addition, LDH, phosphorus, magnesium, creatine kinase (CK), amylase, lipase.
 
b: Blood pregnancy test (women of childbearing potential) once at baseline; further testing at the discretion of the investigator while on study.
 
c: Off-study evaluation performed 4 weeks after removal from study with a window of +/- 7 days
 
d: Day 1 of each cycle while on study. At the investigator's discretion, patients can return for RN/MD visits and get evaluated every 8 or 12weeks after cycle 4. Laboratory assessments and EKG assessments between MD/RN visits can be performed locally with results sent to the study site
 
e: TTE or MUGA will be performed once at week 16 as well as any time felt to be necessary by the investigator. Modalities should remain consistent whenever feasible.
 
f: Scans should be performed every 8 weeks x 4 starting after 2 cycles (e.g. C3D1, C5D1, C7D1, C9D1), then every 12 weeks (C12D1, C15D1, etc). Radiologic documentation must be provided for patients removed from study for progressive disease within 28 days of clinical assessment of progression if no scan was performed within 28 days of the time of that assessment.
 
g: At eye exams the follow tests should be completed : - slit lamp exam - dilated funduscopic exam with photos - optical coherence tomography testing A follow-up eye exam will occur at week 4 (C1W4) and/or if the patient develops new or worsening ocular symptoms
 
h: The timing of pharmacokinetic sample collections is dependent on the treatment schedule the patient is enrolled onto. For treatment schedule A pharmacokinetic sample collections should be drawn at the following timepoints: Cycle 1, Day 1 plasma will be drawn at 0, 1, 2, 4, 6, 8, and 24 hours after taking BGJ398; the 0 and 24 hour timepoints will be drawn before dosing BGJ398. Cycle 1, Day 21 plasma will be drawn 0, 1, 2, 4, 6, and 8 hours after dosing BGJ398. See Table 10.A. These assessments must be done on the exact dates except -3/+1 day window for C1D21 timepoint. Other levels may be drawn as clinically indicated. For treatment schedule B pharmacokinetic sample collections should be drawn at the following timepoints: Cycle 1, Day 1 plasma will be drawn at 0, 1, 2, 4, 6, 8, and 24 hours after taking BGJ398; the 0 and 24 hour timepoints will be drawn before dosing BGJ398. Cycle 1, Day 7 will be drawn at 0, 1, 2, 4, 6, and 8 hours after dosing BGJ398; the 0 hour timepoint will be drawn before dosing BGJ398. Cycle 1, Day 15 will be drawn at 0hr. Cycle 1, Day 21 will be drawn at 0hr. See Table 10.B. These assessments must be done on the exact dates except -2/0 day window for C1D7 and -3/+1 day
													

**MEMORIAL SLOAN-KETTERING CANCER CENTER
IRB PROTOCOL**

IRB#: 14-140 A (7)

	
window for C1D15 and C1D21 timepoint. Other levels may be drawn as clinically indicated.
 
i: For treatment schedule A plasma for imatinib levels will be drawn concurrently with BGJ398 levels at the following two time points: C1D2 (24 hours post-first dose) and C1D21. Both time points will be drawn before dosing imatinib on that day. C1D2 must be done on the exact date, and C1D21 may be drawn within a -3/+1 day window. Other levels may be drawn as clinically indicated.
 
For treatment schedule B plasma for imatinib levels will be drawn concurrently with BGJ398 levels at the following three timepoints: C1D2 (24 hours post-first dose), C1D7 and C1D21. All time points will be drawn before dosing imatinib on that day. C1D2 must be done on the exact date. C1D7 can be drawn within a -2/0 day window and C1D21 can be drawn within a -3/+1 day window. Other levels may be drawn as clinically indicated.
 
j. CBC and Blood Chemistry performed on Day 1 of each cycle must be resulted prior to treatment.
 
All assessments are to be done +/-3 days of the scheduled timepoints unless otherwise noted above. Radiologic assessments (CT, PET, TTE) are to be done +/-7 days from the scheduled appointment.

--	--

Table 10.A: Pharmacokinetic Assessments of BGJ398 on Treatment Schedule A

Treatment Cycle	Day	PK Sample # BGJ398 (Plasma)	Time Relative to Dose
1	1	1	Pre-dose ^a
1	1	2	1hr ± 5 min
1	1	3	2hr ± 5 min
1	1	4	4hr ± 10 min
1	1	5	6hr ± 10 min
1	1	6	8hr ± 15 min
1	2	7	24hr ± 60 min ^a
1	21	8	Pre-dose ^a
1	21	9	1hr ± 5 min
1	21	10	2hr ± 5 min
1	21	11	4hr ± 10 min

**MEMORIAL SLOAN-KETTERING CANCER CENTER
IRB PROTOCOL**

IRB#: 14-140 A (7)

			min
1	21	12	6hr ± 10 min
1	21	13	8hr ± 15 min
Any	Any	101, 102, etc	As clinically indicated

a: These levels should be drawn just prior to administration of BGJ398 plus imatinib on that day

Note: C1D21 will have a -3 days/+1 day window, this window differs from all other PK visits

Table 10.B: Pharmacokinetic Assessments of BGJ398 on Treatment Schedule B

Treatment Cycle	Day	PK Sample # BGJ398 (Plasma)	Time Relative to Dose
1	1	1	Pre-dose ^a
1	1	2	1hr ± 5 min
1	1	3	2hr ± 5 min
1	1	4	4hr ± 10 min
1	1	5	6hr ± 10 min
1	1	6	8hr ± 15 min
1	2	7	24hr ± 60 min ^a
1	7	8	Pre-dose ^a
1	7	9	1hr ± 5 min
1	7	10	2hr ± 5 min
1	7	11	4hr ± 10 min

**MEMORIAL SLOAN-KETTERING CANCER CENTER
IRB PROTOCOL**

IRB#: 14-140 A (7)

1	7	12	6hr ± 10 min
1	7	13	8hr ± 15 min
1	15	14	Pre-dose ^b
1	21	15	Pre-dose ^b
Any	Any	101, 102, etc	As clinically indicated

b: These levels should be drawn just prior to administration of the study drugs (BGJ398 and/or imatinib) on that day

Note: C1D7 will have a window of -2/0 day window, C1D15 and C1D21 will have a -3/+1 day window, these windows differ from all other PK visits

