The primary goal of the phase Ib study is to assess the tolerability and safety of the combination therapy. Once the highest tolerable dose is identified or the clinical doses of imatinib (400 mg daily) and BGJ398 (125 mg qd – three weeks on and one off) are reached, the phase II portion of the study will be initiated. The primary endpoint of the phase II portion is to assess Response Rate (RR) (complete response (CR) + partial response (PR)) by RECIST 1.1.

The phase Ib portion of the study will be performed in standard 3+3 fashion. The phase Ib portion of the study will be open to all patients with locally advanced or metastatic GIST who have progressed on imatinib. An initial cohort of three eligible patients with locally advanced or metastatic GIST will initiate treatment with BGJ398 at 75 mg daily (three weeks on and one off) and imatinib at 400 mg daily for 4 weeks (1 cycle). Depending on the toxicity, dose levels of imatinib (400 mg daily) + BGJ398 will be investigated as outlined below (Table 1). As imatinib 400 mg PO QD is standard of care for metastatic GIST, this dose will remain constant (barring individual dose modifications outlined in section 9.2a).

Table 1: The dose escalation schema:

Dose Level	Imatinib	BGJ395
-2	400mg daily	25 mg qd

MEMORIAL SLOAN-KETTERING CANCER CENTER
IRB PROTOCOL

[figure not shown]
IRB#: 14-140 A (7)

-1	400 mg daily	50 mg qd
1	400 mg daily	75 mg qd
2	400 mg daily	100 mg qd
3	400 mg daily	125 mg qd

Any adverse event that meets criteria in section 9.1 that occurs prior to the second cycle (i.e. before C2D1) will be considered a Dose Limiting Toxicity (DLT) for the purposes of dose escalation to the next dose level. Any adverse event that occurs after the first cycle may require a dose reduction for the patient but will not impact the assessment of dose level safety.

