9.0 TREATMENT/INTERVENTION PLAN

Treatment will be administered on an outpatient basis. Reported adverse events and potential risks are described in Section 11. Appropriate dose modifications of imatinib and BGJ398 are described in section 9.2. No investigational or commercial agents or therapies other than those described below may be administered with the intent to treat the patient's malignancy.

MEMORIAL SLOAN-KETTERING CANCER CENTER IRB PROTOCOL

IRB#: 14-140 A (7)

Imatinib will be self administered orally by the patient on a daily basis throughout the treatment cycle. The standard treatment dose is 400 mg PO QD. 400 mg capsule will be used unless otherwise specified by the treating physician. BGJ398 will be taken at the RP2D and treatment schedule chosen from the Phase Ib portion of the trial. The RP2D selected may be lower than the MTD based on PK data and clinical tolerance beyond Cycle 1. BGJ398 is taken daily for a duration determined by the treatment schedule appropriate for the given dose level. In the event of dose delays of BGJ398, Day 1 of the following cycle will be defined as the day that BGJ398 is restarted. A pill diary for both medications will be provided and recorded (Appendix B). This will be used to assure compliance with the regimen.

On the Phase Ib portion, the timing of pharmacokinetic sample collections will be dependent on the treatment schedule onto which that patient is enrolled. For treatment schedule A pharmacokinetic samples will be drawn on Cycle 1, Day 1 at the following timepoints: 0, 1, 2, 4, 6, 8, and 24 hrs; and Cycle 1, Day 21 at the following timepoints: 0, 1, 2, 4, 6, and 8 hours. For treatment schedule B pharmacokinetic samples will be drawn on Cycle 1, Day 1 at the following timepoints: 0, 1, 2, 4, 6, 8, and 24 hrs; Cycle 1, Day 7 at the following timepoints: : 0, 1, 2, 4, 6, and 8 hours, Cycle 1, Day 15 at timepoint 0hr and Cycle 1, Day 21 at timepoint 0hr.

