**MEMORIAL SLOAN-KETTERING CANCER CENTER
IRB PROTOCOL**

IRB#: 14-140 A (7)

The first three patients will be enrolled at Dose level 1 (Table 1, see section 1) using treatment schedule A. Dose level 1 is chosen based on the standard of care imatinib dose of 400 mg daily in the advanced GIST patient population, and an intermediate dose level of BGJ398 (75 mg daily). This dose is below the BGJ398 MTD of 125 mg daily identified in phase I trials as monotherapy. BGJ398 dose level 1 to -2 will be administered using a schedule of BGJ398 taken daily for 3 weeks followed by one week off and imatinib taken daily throughout the 4 week cycle period (treatment schedule A).

The maximum pace of dose escalation within each cohort is outlined in Table 2. Expansions of lower dose levels may be made based on safety and tolerance considerations at the MSKCC Principal Investigator's discretion, and the selected RP2D may be lower than the MTD defined below. If dose level 1 is not found to be tolerable, then the next cohort will be enrolled at dose level -1. If dose level -1 is not found to be tolerable, then the next cohort will be enrolled at dose level -2. If dose level -2 is not found to be tolerable, then the study may be terminated based on discussions with the MSKCC Principal Investigator. If 0-1 of 6 patients experience a DLT on dose level 3, this will be the RP2D.

Table 2:

Number of Patients with DLT at a Given Dose Level	Escalation Decision Rule
0 out of 3	Enter 3 patients at the next dose level.
1 out of 3	Enter at least 3 more patients at this dose level. 
 • If 0 of these additional 3 patients experience DLT (1/6 total), proceed to the next dose level. • If 1 or more of this group suffer DLT ($\geq 2/6$ total), then dose escalation is stopped, and this dose is declared the MTD. Three (3) additional patients will be entered at the next lowest dose level if only 3 patients were treated previously at that dose.
≥ 2	Dose escalation will be stopped. This dose level will be declared the MTD. Three (3) additional patients will be entered at the next lowest dose level if only 3 patients were treated previously at that dose.
≤ 1 out of 6 at highest dose level below the MTD	This is generally the recommended phase 2 dose. At least 6 patients must be entered at the recommended phase 2 dose (RP2D).

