Using treatment schedule A, if dose level 1 to -2 is identified as the MTD and concern exists regarding therapeutic activity of BGJ398 at this dose level, expansions with higher dose levels (1 to 3) may be considered at the MSKCC PI's discretion, with modification of the treatment schedule. In this setting BGJ398 will be administered daily for one week followed by 3 weeks off and imatinib will be taken

**MEMORIAL SLOAN-KETTERING CANCER CENTER
IRB PROTOCOL**

IRB#: 14-140 A (7)

daily throughout the 4 week cycle period (treatment schedule B). The higher dose level expansion will start by enrolling 3 patients into a cohort, at dose level 1, using treatment schedule B.

When using treatment schedule B the maximum pace of dose escalation within each cohort is outlined in Table2.

Upon documentation of the RP2D dose and treatment schedule of the combination, the phase II trial will open and all subsequent patients enrolled will initiate treatment at that dose and treatment schedule with any subsequent dose modifications as outlined below.

Toxicity will be assessed using the NCI CTCAE (version 4.03) unless otherwise specified. Dose Limiting Toxicity (DLT) is defined as an unexpected adverse event (AE) or abnormal laboratory value assessed as at least possibly related to the study medication, which occurs ≤ 28 days (1 cycle) following the first dose of BGJ398 (cycle 1), and meets any of the criteria listed in Table 3. Please note plasma assessments may substitute for serum assessments per local laboratory standards.

Table 3: Criteria for defining dose-limiting toxicities

TOXICITY	DLT CRITERIA
Hematology	CTCAE grade 4 neutropenia lasting more than 7 consecutive days
	CTCAE grade 4 thrombocytopenia
	CTCAE Grade 3 or 4 neutropenia with fever (temperature $\geq 38.5^{\circ}\text{C}$)
Skin and subcutaneous tissue disorders	Rash, HFSR (Hand Foot Skin Reaction) or photosensitivity CTCAE Grade 3 > 7 consecutive days despite skin toxicity treatment (as per local practice)
	Rash, HFSR or photosensitivity CTCAE Grade 4
Eye disorders	CSR (Central Serous Retinopathy) CTCAE Grade 2 for > 14 consecutive days confirmed by ophthalmologic examination
	CSR (Central Serous Retinopathy) CTCAE Grade ≥ 3 , confirmed by ophthalmologic examination
	Retinal disorder other than CSR (retinal detachment/tear, retinal vascular disorder, retinopathy other) CTCAE Grade ≥ 2 confirmed by ophthalmologic examination

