	Visual disturbances without ocular (retinal) changes: Blurred vision, Flashing lights, Floaters, Corneal abnormalities CTCAE Grade ≥ 3
Gastro-intestinal	\geq CTCAE grade 3 nausea or vomiting ≥ 48 hrs despite optimal anti-emetic therapy
	\geq CTCAE grade 3 diarrhea ≥ 48 hrs despite optimal anti-diarrhea treatment
	Pancreatitis \geq CTCAE grade 3
Hepato-biliary	\geq CTCAE grade 3 total bilirubin
	\geq CTCAE grade 3 ALT (isolated increases in AST without concomitant increases

**MEMORIAL SLOAN-KETTERING CANCER CENTER
IRB PROTOCOL**

IRB#: 14-140 A (7)

	in ALT will not be considered dose-limiting, because of the non-specific nature of AST)
	Serum alkaline phosphatase CTCAE Grade 4 > 7 consecutive days
Investigations (Metabolic)	Serum Lipase and/or serum amylase (asymptomatic) CTCAE grade 3 for > 7 consecutive days Serum Lipase and/or serum amylase (asymptomatic) CTCAE grade 4 Symptomatic serum lipase and/or serum amylase ≥ CTCAE grade 3
ECG QT Interval	QTcF interval ≥ 501 ms on at least two separate ECGs
Renal	Serum creatinine > 2x ULN Serum Phosphorous that requires dose interruption of BGJ398 for >14 days of first 21 days of Cycle 1
Non-hematologic events	≥ CTCAE grade 3, except for the exclusions noted below
Exceptions to DLT criteria	Grade 3 alopecia
	< 5 days of CTCAE grade 3 fatigue
	< 5 days of CTCAE grade 3 edema
	Grade 3 laboratory abnormalities that are responsive to oral supplementation or deemed by the investigator to be clinically insignificant
CTCAE version 4.03 will be used for all grading. Optimal therapy for vomiting or diarrhea will be based in institutional guidelines, with consideration of the prohibited medications listed in this protocol.	

Phase II: The RP2D doses and treatment schedule defined in the phase Ib clinical trial will be used to conduct the phase II portion of the study.

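### If the optional Schedule B is opened, Table 9 requires no ECG on a BGJ398 dosing day within the DLT window, so the QTcF DLT has no required on-dosing reading

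*Combined protocol and SAP*

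**What the plan says.** **Dosing.** The key to Table 9 (Section 10.1.1) gives Schedule B as "BGJ398: Dose as assigned; PO once daily for one week on and 3 weeks off". Section 5.2.3 says missed doses are not made up, so the dosing week is not extended.

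**ECGs.** Table 9 has a single ECG row with entries at pre-study, Week 3 and Week 5, and from Week 9 on Day 1 of each cycle. The window is in the footnotes: "All assessments are to be done +/-3 days of the scheduled timepoints unless otherwise noted above". No footnote adapts the ECG row to the schedule. The pharmacokinetic row, by contrast, is adapted: footnotes h and i and Table 10.B give Schedule B its own cycle-1 Day 7 visit, with samples from 0 to 8 hours.

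**DLT rule.** Table 3 (Section 9.1) lists "QTcF interval ≥ 501 ms on at least two separate ECGs". Section 1.0 sets the window: an event that meets the criteria and "occurs prior to the second cycle (i.e. before C2D1) will be considered a Dose Limiting Toxicity". Section 9.1 gives the window as 28 days, or one cycle.

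**Use of the rule.** Schedule B is discretionary: "expansions with higher dose levels (1 to 3) may be considered" if Schedule A puts the MTD at level 1 or lower and activity is in doubt. Escalation then follows the 3+3 table: "When using treatment schedule B the maximum pace of dose escalation within each cohort is outlined in Table2".

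**The concern.** A 3+3 escalation is only as good as its count of cycle-1 DLTs. The QTcF criterion can be met only if an ECG is recorded, and on Schedule B no required ECG coincides with dosing. QTcF prolongation without symptoms may not prompt an unscheduled ECG, so an event on Days 1 to 7 could go uncounted when the next cohort is opened, at dose levels from 75 to 125 mg. Because the pharmacokinetic draws were adapted to Schedule B and the ECG was not, this looks like an oversight rather than a choice.

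**Working it through.** The plan states no figure on this point, so there is nothing to reproduce. The check compares calendar days.

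**Inputs**
- Schedule B cycle-1 dosing: Days 1–7. Schedule A: Days 1–21 (Table 9 key).
- DLT window: Days 1–28, before C2D1 (Section 1.0; Section 9.1).
- Week labels: the Phase II calendar key (Section 10.1.2) equates week 3 of its blood draws with C1D15 and week 5 with C2D1. I assume the same for Phase Ib. That key also places a week 3 PET scan at C1D21, so Day 21 is shown as an alternative.
- Visit window: ±3 days (Table 9 footnotes).

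**Required ECGs against dosing days**

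| Required ECG | Days with window | Schedule A, in DLT window | Schedule B, in DLT window | Days after last Schedule B cycle-1 dose |
|---|---|---|---|---|
| Week 3 as Day 15 | 12–18 | on drug throughout | off drug throughout | 15 − 7 = 8 (12 − 7 = 5 to 18 − 7 = 11) |
| Week 3 as Day 21 | 18–24 | on drug to Day 21 | off drug throughout | 21 − 7 = 14 (18 − 7 = 11 to 24 − 7 = 17) |
| Week 5 (Day 29) | 26–32 | Days 26–28 are off drug | Days 26–28 are off drug | 26 − 7 = 19 to 28 − 7 = 21 within the window |

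On the Day 15 reading, the number of required on-dosing ECGs inside the DLT window is 0 for Schedule B and 1 for Schedule A.

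**Edge case.** Read literally, 28 days after the first dose could reach Day 29, a dosing day with an ECG. Section 1.0 excludes it. A Day 29 reading would also follow 21 drug-free days and would not observe cycle-1 dosing.

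**Later cycles.** From cycle 2 on, the required ECG is at Day 1 ±3. When it falls on dosing days, it comes no later than the fourth dose of the cycle.

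**Risk context**
- hERG IC50 1121 ng/mL (Section 3.2.2.2); median Day 15 Cmax at 125 mg, three weeks on and one off, 251 ng/mL (Section 3.2.4). Ratio to total Cmax: 1121 / 251 ≈ 4.5.
- With 98% protein binding (Section 3.2.2.1, the animal pharmacokinetics section), free Cmax ≈ 251 × 0.02 = 5.02 ng/mL, and 1121 / 5.02 ≈ 223. This assumes that the binding figure applies to patients and that the IC50 is a free concentration.
- Day 7 Cmax is not given. On the same regimen it was 71.3 ng/mL on Day 1.

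**Patients.** 3 levels × up to 6 = at most 18, assuming no further expansion; 0 if Schedule B is not opened.

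**After the fix.** C1D7 with its −2/0 day window is Days 5–7. All are dosing days inside the DLT window, so the on-dosing count becomes 1.

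**The case against.** The strongest reply is that little depends on this. Schedule B may never open. The animal studies showed no ECG effect, no clinically significant QT prolongation was reported among the 94 monotherapy patients (Section 11.1.2.1), and entry requires QTcF of at most 480 ms. Section 9.4.2 asks for careful monitoring of patients on QT-prolonging drugs or opioids, so unscheduled ECGs will occur. Dose selection also looks past cycle 1: "The RP2D selected may be lower than the MTD based on PK data and clinical tolerance beyond Cycle 1".

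Most of this stands, and it limits the size of the point. It does not remove it. Reassurance from BGJ398 alone is incomplete for the combination: BGJ398 is a CYP3A4 substrate (Section 9.4.2) and Appendix E lists imatinib as a moderate CYP3A4 inhibitor. Tolerance after cycle 1 can inform the RP2D, but it does not enter the count that opens the next cohort.

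A reader might infer that 100 and 125 mg with imatinib would necessarily be given first on Schedule B. Table 2 supports this if taken at its word, because the MTD is the level that stopped escalation: "Dose escalation will be stopped. This dose level will be declared the MTD". An MTD of level 1 then means that Schedule A stopped at 75 mg. Section 14.0, however, uses MTD in the ordinary sense, as a dose to which patients may be raised. On that sense an MTD of level 1 means 100 mg was already given on Schedule A, with an on-drug Week 3 ECG, and only 125 mg would be new. The documents do not settle which sense applies.

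A reader might also infer that Table 7 needs rewriting, because its follow-up ECGs copy the cycle-1 frequency. Frequency means how often, Table 7 allows ECGs as clinically indicated, and later Day 1 ECGs already fall in Schedule B dosing weeks. Tying the phrase to Day 7 would create attendances in cycles 2 and 3 that Table 9 does not contain.

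**Conclusion.** The gap is real and specific to Schedule B: there is no required ECG on any of the seven cycle-1 dosing days, and the one required post-baseline ECG comes 5 to 11 days after the last dose (up to 17 if a site uses Day 21). The QTcF DLT therefore has no required on-dosing reading for Table 2 escalation.

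The conclusion rests on reading Week 3 by analogy with the Phase II calendar; either reading leaves the count at zero. It concerns required ECGs only. It does not show that the Day 15 ECG is uninformative: no human half-life for BGJ398 is given, so residual drug cannot be excluded, and imatinib continues daily. Nor does it show that QT events are likely or that Schedule B is unsafe. At most about 18 patients are involved. This should be corrected before Schedule B opens because the correction is cheap, not because a safety signal is expected.

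**What to change.** Add one footnote to Table 9, for Schedule B only: the cycle-1 Week 3 ECG is done at the existing C1D7 pharmacokinetic visit (−2/0 days), 2 to 4 hours after the BGJ398 dose. This matches the reported Tmax of 2–3 hours and sits beside the 2- and 4-hour plasma samples.

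No separate repeat rule is needed. Table 7 already calls for hourly ECGs when QTcF exceeds 500 ms, which supplies the second ECG that Table 3 requires. Leave Table 7 unchanged, including its reference to the cycle-1 frequency, so that no Day 7 visit is created in later cycles. Schedule A, the Day 1 ECGs and all DLT, dose and hold rules stay as they are.

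Cost: one footnote, with no added cycle-1 visit or scheduled test. The downside is losing the off-drug Day 15 ECG, which pairs with the Day 15 plasma sample, unless a site chooses to keep it.

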5.2.3 Administration of BGJ398

BGJ398 will be taken orally, using treatment schedule A (once a day for 21 days on, 7 days off) or treatment schedule B (once daily for 7 days on, 21 days off) repeating in 28 day cycles. Patients should be instructed to take the daily dose of BGJ398 in the morning, at approximately the same time each day (24 ± 2 hour interval). Patients should consume a light breakfast each day (e.g., non-grapefruit-based juice, toast and jam). This should be followed by a 2 hour fast, after which the doses of study drug should be taken. Patients should continue to fast for 1 hour after the administration of study drug.

BGJ398 should be taken with a large glass of water (~250 mL) and consumed over as short a time as possible. Patients should be instructed to swallow the capsules whole and not chew them. If for any reason a breakfast was not consumed prior to taking the dose the patient should take the dose with a full glass of water, and continue to fast for an hour after taking the dose. If the patient forgets to take the scheduled dose in the morning, he/she should not take the dose more than 2 hours after the usual time and should continue treatment the next day. Any doses that are missed should be skipped altogether and should not be replaced or made up at the next scheduled dosing.

If vomiting occurs following the dosing of study drug, re-dosing is not permitted that same day. Dosing should resume the next day. BGJ398 is characterized by pH-dependent solubility, and therefore, medicinal products that alter the pH of the upper gastro-intestinal tract may alter the solubility of both compounds, and limit bioavailability. These agents include, but are not limited to, proton-pump inhibitors (e.g., omeprazole), H₂-antagonists (e.g., ranitidine) and antacids. Therefore, BGJ398 should be dosed at least 2 hours before or 10 hours after dosing with a gastric protection agent. Patients must avoid consuming Seville oranges or juice, grapefruit, grapefruit juice, grapefruit hybrids, or pummelos from 7 days prior to the first dose of study medication through the end of study participation. This is due to a potential CYP3A4 interaction with study medication. Normal oranges and orange juice are allowed.

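### On Schedule A, the +1 day of the C1D21 pharmacokinetic window is Day 22, the first off-drug day, so a visit on that day cannot give the BGJ398 post-dose profile

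*Combined protocol and SAP*

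**What the plan says.** **Dosing.** Section 5.2.3 describes "treatment schedule A (once a day for 21 days on, 7 days off", repeating every 28 days. The key to Table 9 (Section 10.1.1) agrees: "YA: BGJ398: Dose as assigned; PO once daily for 3 weeks on and one week off". The Schedule A row of Table 9 shows no BGJ398 in Week 4. Section 5.2.3 also says that missed doses are not made up.

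**Sampling.** Table 9 footnote h says: "Cycle 1, Day 21 plasma will be drawn 0, 1, 2, 4, 6, and 8 hours after dosing BGJ398". Table 10.A times these six samples relative to dose, and its note on the pre-dose sample reads "These levels should be drawn just prior to administration of BGJ398 plus imatinib on that day".

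**Window.** Footnote h: "These assessments must be done on the exact dates except -3/+1 day window for C1D21 timepoint". Table 10.A: "C1D21 will have a -3 days/+1 day window, this window differs from all other PK visits". Footnote i gives the same window to the Schedule A imatinib trough, which is drawn together with the BGJ398 sample.

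**Schedule B, for comparison.** The matching profile on the last dosing day is C1D7. The note to Table 10.B says "C1D7 will have a window of -2/0 day window", with no plus side.

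**Use of the data.** Section 14.0 lists BGJ398 AUC and Cmax as a Phase Ib secondary endpoint and summarises plasma concentrations as mean +/- SE. Section 9.0 says: "The RP2D selected may be lower than the MTD based on PK data and clinical tolerance beyond Cycle 1".

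**The concern.** A site can keep to the sampling window and still be unable to collect what the sampling table asks for. Day 22 is a permitted visit day, but no BGJ398 is due then and nothing in the protocol excludes that day. The samples labelled 1 to 8 hours would have no same-day dose to be timed from.

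On Schedule A, the starting schedule, C1D21 is the only scheduled multiple-dose BGJ398 profile. The Day 1 profile cannot replace it, because exposure rises with repeated dosing. Section 3.2.4 reports median AUC over 24 hours, at 125 mg three weeks on and one week off, of about 632 h.ng/mL on Day 1 and 3693 h.ng/mL on Day 15. At stake is a secondary endpoint estimated in small cohorts that may also inform the choice of a recommended Phase II dose below the MTD.

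Day 22 is not a far-fetched visit day. It is the first day of Week 4, for which Table 9 schedules a physical examination, blood counts, chemistry and an eye examination.

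**Working it through.** The plan gives no figure to reproduce. The check is calendar arithmetic.

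**1. Window against dosing days, Schedule A**
- Window (footnote h, Table 10.A note): 21 - 3 = 18 to 21 + 1 = 22, so Days 18, 19, 20, 21 and 22.
- On-drug days (Section 5.2.3, Table 9 key): Days 1 to 21.
- Overlap: Days 18 to 21, or 4 of 5 permitted days. Day 22 is off drug: 1 of 5.

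**2. What a Day 22 visit yields**
- Assume the Day 21 dose was taken at the usual time and none on Day 22.
- The nominal 0, 1, 2, 4, 6 and 8 h draws fall about 24 + 0, 1, 2, 4, 6 and 8 = 24, 25, 26, 28, 30 and 32 h after the last dose.
- The first is a usable 24-hour trough. The other five are an elimination tail, from which no post-dose Cmax or AUC over 0 to 8 h can be taken.

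**3. The same test on the neighbouring samples**

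| Sample | Window | Days | Same-day dose needed | Given on every permitted day? |
|---|---|---|---|---|
| Schedule A C1D21, BGJ398 profile | -3/+1 | 18-22 | BGJ398 | No, fails on Day 22 |
| Schedule A C1D21, imatinib trough | -3/+1 | 18-22 | Imatinib (daily) | Yes |
| Schedule B C1D7, BGJ398 profile | -2/0 | 5-7 | BGJ398 | Yes |
| Schedule B C1D21, single 0 h sample | -3/+1 | 18-22 | No BGJ398 dose (off drug since Day 7) | Not applicable |

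Only the Schedule A BGJ398 profile fails.

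**4. Size for one patient seen on Day 22**
- Profile dropped: 1/3 = 33% of a cohort of 3, or 1/6 = 17% of a cohort of 6.
- Day 1 is no substitute: 3693/632 = 5.8-fold higher median AUC by Day 15.
- Profile kept under the C1D21 label: suppose patients are otherwise alike and the undosed patient's level is a fraction f of the true post-dose level. The mean then falls by (1 - f)/n.
  - The most it can fall is 1/n (f = 0): 33% for n = 3, 17% for n = 6.
  - For the other end, take the Section 3.2.4 Day 15 medians at 125 mg on this schedule. The 24-hour average is 3693/24 = 154 ng/mL against a Cmax of 251 ng/mL, and 154/251 = 0.61. Levels from 24 h onward should lie below that average, so at the peak f is at most about 0.61 and the fall is at least about 0.39/3 = 13% or 0.39/6 = 6%.
  - This is illustrative: it combines medians from BGJ398 given alone.

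**5. After the fix**
- A -3/0 window covers Days 18 to 21, so 4 of 4 permitted days are on drug.

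**The case against.** Several points on the other side stand.

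- **Most of the window works.** A reader might infer that the whole C1D21 window is unsound. It is not: Days 18 to 21 all give a dosed profile.
- **Bias is not certain.** A reader might infer that the dose-level means will be pulled down. Sections 5.2.3 and 9.0 require doses to be recorded in a diary, and Table 10.A times samples from a dose, so an undosed draw can be recognised. Loss of the profile is the likelier outcome. Bias needs an analyst to retain the draw under its nominal label, and Section 14.0 has no rule against that.
- **No extra dose is authorised.** A reader might infer that the window invites a BGJ398 dose on Day 22. A sampling window permits no dosing; such a dose would be a separate departure from the schedule.
- **The role of the data is limited.** BGJ398 PK is a secondary endpoint with no formal test. Escalation follows toxicity counts in Table 2, and PK is one optional input to the dose choice. The 33% figure does not apply to a completed cohort at the recommended dose, since Table 2 requires at least 6 patients there.
- **The BGJ398 window cannot be changed alone.** Footnote i has the imatinib trough drawn concurrently, and the lab manual (Appendix I) uses one blood tube per timepoint with an added aliquot for imatinib. Leaving +1 for imatinib only would split that draw.

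None of this removes the inconsistency. The window is stated in two places, Day 22 is within both, and no text excludes Day 22 or provides a BGJ398 dose on it.

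**Conclusion.** The point holds for the +1 day only. One of the five days permitted for the Schedule A C1D21 profile is off drug, and a visit on it loses five of six samples and the patient's only scheduled multiple-dose BGJ398 profile. The Schedule B C1D7 window shows that the protocol can set a window that ends on the last dosing day.

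The size is conditional: 33% or 17% of a cohort's multiple-dose profiles for each patient seen on Day 22, or lower post-dose means if the draws are kept. The documents give no expected frequency, so no overall loss can be stated. The conclusion assumes that Schedule A dosing ends on Day 21 as written and that the patient was otherwise taking BGJ398 as scheduled.

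The Day 1 profile, dose-limiting toxicity assessment and the Phase II primary endpoint are untouched. This should be corrected, but it does not threaten the trial's main conclusions.

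**What to change.** - Set the Schedule A C1D21 PK window to -3/0 days in Table 9 footnote h and in the note to Table 10.A.
- Make the same change in footnote i for the Schedule A imatinib trough, so that the single shared draw in the lab manual is preserved.
- Leave the Schedule B C1D21 window at -3/+1; it causes no difficulty.
- State in Section 14.0 that any draw without a same-day BGJ398 dose is excluded from C1D21 AUC and Cmax.

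The cost is three edits to window wording, one added analysis sentence, and one day less scheduling flexibility for Schedule A sites. The change concerns sampling and analysis only; no change to dosing is proposed.
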